8.3.1 Sponsor and Investigator Reporting, Notifying Reviewing IRBs

The site investigators will report to their reviewing IRB according to local policy and procedure.

MCR Site

The regulatory sponsor or designated study staff will report to the Mayo Clinic IRB any UPIRTSOs originating at MCR (see Section 8.1 for definition of UPIRTSO) according to Mayo Clinic IRB policy and procedures. Non-UPIRTSOs occurring at MCR and any adverse events occurring at other site(s) will be reported to the Mayo Clinic IRB at the time of continuing review, according to the Mayo Clinic IRB policy and procedures.

For any adverse event occurring at MCR, study staff will firstly follow procedures to protect the study subject. The regulatory sponsor will assess and determine if the problem or event meets *all three* criteria for a UPIRTSO and whether any modifications to the study protocol are necessary. If the problem or event *does* meet criteria for a UPIRTSO, the Mayo Clinic IRB will be notified within five working days of knowledge of the problem or event. The regulatory sponsor will also include a corrective action plan or justification as to why a plan is not needed. If necessary, a protocol modification will be submitted to Mayo Clinic IRB. If a protocol modification is deemed necessary, the regulatory sponsor will notify the FDA, DSMB, and the MUSC site PI within five working days. Site investigators will be responsible for ensuring that no participants are enrolled at either site until such modifications have been approved by the respective IRBs. All UPIRTSOs occurring at MCR will be reported to MUSC at the time of FDA and Mayo Clinic IRB reporting. All MCR Non-UPIRTSOs will be reported to MUSC at least yearly or earlier upon request.

MUSC Site

The MUSC PI or designated study staff will report to the MUSC IRB any Unanticipated Problems (see Section 8.1 for definition of Unanticipated Problem) originating at MUSC according to MUSC IRB policy and procedures. Events or effects that do not meet the definition of Unanticipated Problems will be reported to the MUSC IRB at the time of continuing review.

For any adverse event occurring at MUSC, study staff will firstly follow procedures to protect the study subject. The site PI will then assess the severity and relatedness of the study treatment to the event and notify the regulatory sponsor as follows. For events suspected to meet criteria for a UADE (see section 8.1) or a severe, expected AE at least probably related to the study treatment, the regulatory sponsor will be notified within 24 hours of learning of the event. For suspected moderate or mild, expected AEs, the

regulatory sponsor will be notified as soon as possible but in no event more than three working days of the event. The regulatory sponsor will then be responsible for assessing the event and determining the subsequent follow-up and reporting requirements.

If a protocol modification is deemed necessary by the MUSC IRB, the site PI or designated study staff will notify the regulatory sponsor within five working days. The regulatory sponsor will be responsible for submitting these modifications to the FDA, Neuronetics, the DSMB, and Mayo Clinic IRB. No participants will be enrolled at either site until such modifications have been approved by the respective IRBs.

8.3.2 Regulatory Sponsor Reporting: Notifying the FDA

The regulatory sponsor will report to the FDA all unanticipated adverse device effects according to the required reporting timelines, formats, and regulations.

The regulatory sponsor will submit a completed FDA Form 3500A to the FDA's Center for Devices and Radiological Health for any observed or reported adverse effect that is determined to be an unanticipated adverse device effect. A copy of this completed form will be provided to the DSMB and all participating sub-investigators. The completed FDA Form 3500A will be submitted to the FDA no later than 10 working days after the regulatory sponsor first receives notice of the UADE.

If the results of the regulatory sponsor's follow-up evaluation show that an adverse effect that was initially determined to not constitute a UADE does in fact meet the requirements for reporting, the regulatory sponsor will submit a completed FDA Form 3500A no later than 10 working days after the determination was made.

For each submitted FDA Form 3500A, the regulatory sponsor will identify all previously-submitted reports that addressed a similar adverse effect experience and will provide an analysis of the significance of the newly reported adverse effect in light of any previous, similar report(s).

Subsequent to the initial submission of a completed FDA Form 3500A, the regulatory sponsor will submit additional information concerning the reported adverse effect as requested by the FDA.

Reporting Process

Unanticipated Adverse Device Effect reports will be submitted on FDA Form 3500A. The contact information for submitting reports is:

Food and Drug Administration
Center for Devices and Radiological Health
Document Mail Center - WO66-G609
[name]
Silver Spring, Maryland 20993-0002

Deviations from the investigational plan.

An investigator shall notify the regulatory sponsor and reviewing IRB of any deviation from the investigational plan to protect the life or physical well-being of a subject in an emergency. Such notice shall be given after the emergency occurred within reporting timeframe outlined by the site IRB. Except in such an emergency, prior approval from the

regulatory sponsor is required for changes in or deviations from a plan. In addition, if these changes or deviations may affect the scientific soundness of the plan or the rights, safety, or welfare of human subjects, FDA and IRB notification in accordance with 21 CFR 812.35(a) also is required.

8.4 Unblinding Procedures (Breaking the Blind)

While the safety of the subject always comes first, it is still important to seriously consider if unblinding the study therapy is necessary to ensure a subject's safety. In the event of a serious adverse device effect, the investigator will carefully assess whether breaking the blind will critically affect how a subject is treated in response to the adverse effect and whether this knowledge outweighs the implications to the scientific soundness of the study. In the case of most serious adverse effects, treatment would be discontinued and symptoms treated symptomatically irrespective of the knowledge of whether the treatment received was active or sham in nature. In these instances, having this information would not significantly alter the treatment of the adverse effect(s).

As an additional safeguard against bias, the DSMB has been charged with making the final recommendations for breaking the study blind. If the DSMB recommends unmasking the study, Neuronetics, Inc. will be contacted and the key to active or sham treatment will be obtained. Notation regarding the nature of the treatment the subject had been receiving will be documented in the subject's source document.

If the decision to break the blind is made immediately upon learning of the adverse event, this information will be reported to the FDA and reviewing IRB at the time of initial adverse event reporting. If the unblinding occurs after the initial reporting, the FDA will be notified of the action within ten working days from the time of breaking the blind. The reviewing IRB will be notified according to their reporting guidelines if the decision is made to break the study blind after the initial reporting.

If unblinding occurs at one site, the other site WILL NOT be given the randomization key unless directed to do so by the FDA; Neuroentics, Inc.; reviewing IRB; or the DSMB.

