5.1 Description

The NeuroStar TMS Therapy® System is a computerized electromechanical instrument that produces and delivers brief duration, rapidly alternating (pulsed) magnetic fields to induce electrical currents in localized regions of the cerebral cortex. It is a non-invasive tool used for the treatment of patients with MDD who have not achieved clinical response from one prior adequate trial of antidepressant pharmacotherapy (see Appendix J3 for detailed product description and use). The NeuroStar TMS Therapy™ System has been FDA-approved for use in adult patients. NeuroStar XPLOR™ is a clinical research option for the NeuroStar TMS Therapy System that provides features necessary to conduct randomized, controlled trials and other TMS research. Active treatment modality is essentially the same for both the NeuroStar TMS Therapy™ System and NeuroStar XPLOR™. See Appendix J4 for description of NeuroStar XPLOR device.

The NeuroStar XPLOR TMS System consists of the following equipment and software:

- Mobile Console (includes processor module, power module, mast, gantry, halo, and display arm)
- System Software; the XPLOR option also includes a dedicated system software

- application (software version 1.7.5 or greater) with its own dedicated database of patient/subject treatment history, TrakStar application, and TrakStar database that operates only with the corresponding XPLOR Software, maintaining isolation, security, and data integrity of the research
- Practice Data Management System (PDMS) software
 - Therapy Coils; included with the XPLOR option is a set of three TMS coils:
 - a blinded sham or placebo coil; the sham coil is acoustically matched to protect the integrity of the blind,
 - a blinded active coil, and
 - a standard treatment coil that can be used for performing motor threshold level determination or open-label treatment.
 - Head Support System (includes laser positioning aid and coil positioning guide)
 - Treatment Chair
 - Positioning Cushions (to enhance comfort and positioning of the patient in the required posture for the duration of the treatment session)

The NeuroStar TMS System also requires supplies and disposables for each treatment session:

- Head Cushion Liner
- Head Side Pad Liner
- Head Positioning Straps
- Earplugs
- SenStar Treatment Link (a single-use medical device)
- Used SenStar Treatment Link Return Box

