5.2 Method for Assigning Subjects to Treatment Groups

Enrolled subjects will be assigned to either the blinded sham coil or the blinded active coil during Phase I of the study using a permuted block randomization method, with the result of the same number of subjects being assigned to both treatment groups. The randomization schedule will be generated by the Mayo Clinic Health Sciences Research (HSR) Biostatistical team. Once generated, the randomization assignment for each subject receiving treatment will be printed on a separate card and sealed in an envelope prepared by the HSR team. These envelopes will be unsealed and subjects will be randomized to the study prior to their first treatment, but not before informed consent/assent has been obtained, they are confirmed to be eligible for the study, and all baseline visit requirements have been fulfilled. In this way, selection bias can be avoided should study staff deduce the nature of the blinded coils. For safety precautions, the full randomization schedule will be sent to the chair of the Data Safety Monitoring Board by the HSR team. In addition, study staff will keep a spreadsheet of the subject number associated with each randomization number, so that the DSMB may unblind a specific subject in the event of a medical emergency.

The XPLOR software has built-in checks that, once a subject has been randomized to a particular coil, will prevent treatment from taking place with the incorrect blinded coil. This safety precaution provides blinding to the staff applying study treatment, staff performing the mood, cognitive, safety, and imaging assessments, and to the subjects – essentially creating a triple-blinded procedure.

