5.7 Blinding of Study

The blinded TMS coils will arrive from Neuronetics and will be identical in appearance and labeled generically (i.e Coil X and Coil Y). The device will recognize one coil as active and the other coil as sham. Once a participant has been randomized, the device will “link” the participant’s treatment with the corresponding coil. The device will remain inactive if the “incorrect” coil is used for a subject, adding an additional safeguard for each participant and the integrity of the study and allow the treaters to remain blinded to the nature of the subject’s treatment.

As outlined in protocol Section 5.2, subjects will be randomly assigned to a coil and will receive all treatments during Phase I of the trial using this coil. Neither the subject nor the study staff (including those administering rTMS treatments and those administering mood, cognitive, safety, and imaging assessments) will know whether the subject is receiving active or sham treatment.

In Phase II of the trial, based upon clinical response in Phase I, subjects will be assigned to either Acute Treatment (Arm 1) or Maintenance Treatment (Arm 2). All treatments during phase II will be provided with the known-active coil.

To minimize any source of bias, unblinding of the study will not be done until all subjects have completed both Phase I and Phase II treatments. However, unblinding will occur if the Data and Safety Monitoring Board deems it necessary due to critical, unexpected patient care considerations (such as in the event of a high rate of unexpected serious adverse events).

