8.6.1 Internal Data and Safety Monitoring Board

A Data and Safety Monitoring Board will be assembled to oversee the safety of the study, patients, and the scientific validity and integrity of data collected as part of the study. This DSMB will include members representing both sites and will consist of at least one non-study, Board-certified psychiatrist and at least one non-study, pediatric neuropsychologist. The DSMB will meet bi-annually to review any adverse events related to the study, ensure that appropriate actions were taken by study staff, the event resolved, and the proper agencies notified. If deemed necessary, the DSMB will make recommendations for changes to the study protocol to ensure the continued safety of study subjects and integrity of study data collected. All serious adverse events will be reviewed monthly or sooner upon request. In the event of an SAE, this DSMB has also been charged with making the final decision regarding breaking the study blind. Whenever possible, the DSMB will work directly with Neuronetics and the subject's clinical physician without involving the study physicians in order to prevent study bias.

9 Data Handling and Record Keeping

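### Section 8.4 puts an unblinded subject's arm in that subject's source document, which can decode other subjects at the site and conflicts with section 8.6.1

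*Combined protocol and SAP*

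**What the plan says.** Section 5.1 describes the hardware: "included with the XPLOR option is a set of three TMS coils", of which two are blinded (one active, one sham) and the third is the open coil. Section 5.7 says the blinded coils arrive "labeled generically (i.e Coil X and Coil Y"). It adds: "The device will recognize one coil as active and the other coil as sham". It also says that "subjects will be randomly assigned to a coil and will receive all treatments during Phase I of the trial using this coil". The device will not run if the wrong blinded coil is fitted.

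Section 5.2 sends the full randomization schedule to the DSMB chair. It also has staff keep a list linking subject and randomization numbers, "so that the DSMB may unblind a specific subject in the event of a medical emergency".

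Section 8.4 gives the DSMB the final recommendation on breaking the blind. If it recommends a break, the manufacturer supplies the key. The instruction that follows is "Notation regarding the nature of the treatment the subject had been receiving will be documented", and the place named is that subject's source document. The other site does not receive the key unless an oversight body or the manufacturer directs it.

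Section 8.6.1 says the DSMB should, where possible, deal with the manufacturer and the subject's own physician "without involving the study physicians in order to prevent study bias".

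**The concern.** Section 8.6.1 aims to keep the result of a blind break away from the study physicians. The recording rule in section 8.4 places the result in a file that site staff work in. With only two labels, that entry is informative about more than one subject.

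The outcomes at stake are clinician ratings. The primary outcome measures include the CDRS-R and CGI-I, and response in section 7.2 also uses the CGI-S. If knowledge of the arm reached raters, later Phase I ratings at that site could be influenced by it. Section 7 has no analysis that would show whether this mattered.

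**Working it through.** The plan states no figure on this point, so there is none to reproduce. The check is a reading of the sections together, followed by a count.

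**1. What one disclosure reveals.** The key at a site has two possible states: X active and Y sham, or X sham and Y active. One subject's label and arm, taken together, rule out one state, leaving 2 − 1 = 1. The key is then known. It applies to every subject at that site whose label is known, including those randomized later. Both facts are needed: an arm without labels, or labels without an arm, does not give the key.

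**2. Who knows the labels.** Under section 5.7 the device stays inactive with the wrong coil, so whoever fits the coil must know which one the subject needs. Section 5.2 itself allows for leakage, saying that "selection bias can be avoided should study staff deduce the nature of the blinded coils". The safeguard there is sealed envelopes, which protect assignment and not later ratings. No section says whether raters know the labels.

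**3. Who could see the arm.**

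| Section | Provision | Effect |
|---|---|---|
| 8.6.1 | DSMB bypasses study physicians where possible | Keeps the arm from them |
| 8.4 | Arm noted in the subject's source document | Puts the arm in a site record |
| 8.2 | Adverse events recorded in the source document | Investigators use that record |
| 9.3 | Daily treatment summary stored there; study staff transcribe source data to the eCRF | Other staff use that record |
| 8.4 | Other site not given the key | Protects the other site only |

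No supplied text seals the entry or limits who may read it.

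**4. Other routes.** Section 8.4 requires a blind break to be reported to the FDA and the reviewing IRB. Under section 8.3, site investigators or study staff report to their own IRB. Under section 8.3.2, the regulatory sponsor reports to the FDA and copies of the form go to the sub-investigators. Section 4.3.1 shows that the regulatory sponsor is also the MCR site investigator. The text does not say whether these reports state the arm, but nothing prevents it.

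**5. How many subjects.** The planned site sizes in the Study Summary are 50 and 25, for a total of 75.

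- MCR: 50 − 1 = 49 others.
- MUSC: 25 − 1 = 24 others.

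These are maxima. If *k* of the other subjects have already finished their Phase I ratings, the exposed number is 49 − *k* or 24 − *k*. It therefore ranges from 49 (or 24) down to 0. As an illustration only, if half had finished, the numbers would be 49/2 = 24.5 and 24/2 = 12.

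**The case against.** The strongest reply is that the plan foresees this and accepts it. Section 8.4 makes the investigator weigh the scientific cost before a break and contains the key at one site. Section 8.5 reserves unmasking for extreme circumstances or a high level of side effects attributed to rTMS. The DSMB chair holds the schedule and could inform the subject's own physician without anyone at the site learning the arm. On this view section 5.2 is right that one subject can be unblinded. All of this stands. The difficulty arises only when the result reaches people who know the labels, and the recording rule in section 8.4 makes that possible.

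A reader might infer that one unblinding turns the rest of the site's ratings into open-label ratings. The documents do not support that. The note goes into one subject's file, and no section says that raters read that file or know coil labels.

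A reader might also take the site shares, 50/75 = 67% and 25/75 = 33% of the trial, as the exposure. Those figures count the unblinded subject and assume that no other subject at the site has completed Phase I ratings.

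Finally, Appendix N, on the DSMB, is listed but its text is not among the supplied documents. It may contain rules on custody of the result, so the absence of a restriction can be asserted only for the text available.

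**Conclusion.** The concern holds in limited form. Sections 8.4 and 8.6.1 pull in opposite directions. Because there are two labels for two arms, the entry that section 8.4 requires can disclose the arms of other subjects at the same site to anyone who knows their labels. Treaters do; for raters the documents are silent.

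The probability is low. The exposure is at most 49 other subjects at MCR or 24 at MUSC, less those whose Phase I ratings are complete. Whether any rating would actually be biased cannot be determined from the documents.

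The conclusion rests on three assumptions: one blinded coil pair per site, which sections 5.1, 5.7 and 5.8.3 imply but do not state; planned enrollment at each site; and no custody rule in the unseen appendix. It is a cheap improvement to a contingency rule and does not call the main design into question.

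**What to change.** 1. Reconcile section 8.4 with section 8.6.1. The source document should record the date and the fact of unblinding, without the arm. The arm should be held until database lock in a restricted record kept by the DSMB or the HSR statistician.
2. Apply the same restriction to FDA and IRB reports that pass through site staff (sections 8.3, 8.3.2 and 8.4). Changing the source-document sentence alone would leave those routes open.
3. Leave emergency access to the arm for the sponsor to settle when reconciling the two sections. This point proposes no rule for it.
4. Prespecify in section 7 a sensitivity analysis that excludes Phase I ratings made at that site after any unblinding. State how excluded ratings are handled, since the primary analysis in section 7.1 carries the last observation forward.

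The cost is a short edit to section 8.4 and the reporting sections, plus one analysis that is needed only if a break occurs. Routine study staff lose direct access to the result. Hardware, randomization and sample size do not change.

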8.5 Stopping Rules

Specific occasions when study treatment may be stopped are explained in the discussion of risk management (section 1.4.2).

Because of the anticipated low level of adverse events of rTMS, the DSMB will be charged with reviewing adverse events every six months. Serious adverse events will be reviewed on a monthly basis, unless a more urgent review is requested. Only under extreme circumstances or if it were determined that a high level of side effects was due to rTMS, would the DSMB be charged with breaking the study mask.

8.6 Medical Monitoring

The regulatory sponsor has oversight for the overall safety of the study. This safety monitoring will include careful assessment and appropriate reporting of adverse events as noted above, as well as the construction and implementation of a data and safety-monitoring plan. Medical monitoring will include a regular assessment of the number and type of serious adverse events.

8.6.1 Internal Data and Safety Monitoring Board

A Data and Safety Monitoring Board will be assembled to oversee the safety of the study, patients, and the scientific validity and integrity of data collected as part of the study. This DSMB will include members representing both sites and will consist of at least one non-study, Board-certified psychiatrist and at least one non-study, pediatric neuropsychologist. The DSMB will meet bi-annually to review any adverse events related to the study, ensure that appropriate actions were taken by study staff, the event resolved, and the proper agencies notified. If deemed necessary, the DSMB will make recommendations for changes to the study protocol to ensure the continued safety of study subjects and integrity of study data collected. All serious adverse events will be reviewed monthly or sooner upon request. In the event of an SAE, this DSMB has also been charged with making the final decision regarding breaking the study blind. Whenever possible, the DSMB will work directly with Neuronetics and the subject's clinical physician without involving the study physicians in order to prevent study bias.

9 Data Handling and Record Keeping

